9.2. Concomitant Medications

Concomitant medications (other than prohibited concomitant medications listed in [Section 9.2.1](#)) will be used at the discretion of the usual care provider (or Investigator if also the usual care provider). Relevant information about all concomitant medications (including prescribed, over-the-counter, or herbal preparations) taken prior to (ie, within 30 days of Screening) and during the study must be recorded in the source documents and CRF, as well as any dose or dose regimen changes that occur during the study. Concomitant medications should be stable prior to Day 0.

Drug Interactions

Subjects taking bile acid sequestrants (BAS, including cholestyramine and its derivatives, colestipol, colesevelam, or other sequestrants) or aluminum hydroxide- or smectite-containing antacids should be instructed to stagger their dosing of investigational product and UDCA, ensuring at least 4 hours between doses of the BAS and/or these antacids and the investigational product (and UDCA; ie, BAS should be administered at minimum 4 hours before or 4 hours after investigational product administration).

OCA taken concomitantly with warfarin may result in decreased INR levels, therefore, INR should be monitored and the dosage of warfarin adjusted, as needed during treatment with OCA and after cessation of OCA, to maintain the target INR range.

The effect of OCA on drug metabolizing enzymes has been evaluated in both in vitro and clinical studies. The PK profile of caffeine, a sensitive CYP1A2 substrate probe, showed weak effect of OCA on CYP1A2. Based on these results, OCA may increase the exposure of narrow therapeutic index drugs that are substrates for CYP1A2, such as theophylline and tizanidine.

Information related to additional drug-drug interaction (DDI) studies is available in the current version of the Investigator's Brochure (IB). The aforementioned sections of the IB should be referred to during the course of the study, and are accessible to investigators to help facilitate the assessment of potential drug-drug interactions with OCA that may be observed in study subjects.

PBC-Specific Therapy

In general, Investigators will be encouraged to follow guidelines for care based upon local and institutional practice patterns and any relevant published practice guidelines. Throughout the course of the study, Investigators are expected to monitor subjects' PBC regimens and, if responsible for usual care, may adjust the regimen in order to achieve locally-appropriate treatment goals. These goals will be individualized, with the understanding that currently applicable PBC guidelines may vary among different geographic regions.

Ideally, subjects should generally remain on the baseline PBC therapies throughout the course of the study, unless the baseline PBC therapy is no longer considered clinically appropriate by the Investigator. In addition, subjects should be reminded to keep taking their blinded investigational product.

9.2.1. Prohibited Medications

Commercial OCA therapy (if available) is prohibited while on investigational product, and if prescribed during the course of the study, the Investigator should be cognizant of the possibility of double dosing. Subjects who continue with commercial OCA therapy must discontinue study medication and are expected to continue through the end of the study (see [Section 9.7.18](#)). The study will only terminate at the time when the needed number of adjudicated events has accrued or at the discretion of the Sponsor. Subjects will need to complete EOT procedures but continue with regularly scheduled visits until the study is terminated (see [Section 9.7.18 Early Discontinuation and/or Early Termination Procedures](#)).

9.3. Treatment Compliance

The Investigator should assess the subject's compliance with dosing of investigational product at each study visit, and confirm by conducting investigational product accountability (ie, count of returned tablets).

Subjects should be instructed to complete a dosing diary to help monitor compliance to the prescribed dosing regimen. Subjects should be instructed to retain all bottles of investigational product, even if empty, and to return them to the Investigator at the subsequent visit. The Investigator or designee should perform investigational product accountability and, if applicable, follow up with the subject to retrieve any investigational product bottles that have not been returned.

If the Investigator has concerns about a subject's dosing compliance s/he should discuss this with the subject, assess the reasons for noncompliance and the likelihood that the subject will remain noncompliant, and notify the Sponsor accordingly.

9.4. Randomization and Blinding

This study will be conducted in a double-blind, placebo-controlled manner. Allocation to one of two treatment groups (OCA or placebo) will occur on a 1:1 ratio across sites and will be stratified by UDCA treatment (yes/no) and mean baseline bilirubin categories ($>ULN/\leq ULN$), as specified by the central laboratory. The randomization will be based on a predefined randomization code (generated by the Sponsor or designee) using an interactive web response system (IWRS), which the Sponsor intends will serve as a computer-based subject registration system at Screening and Day 0. The IWRS will serve as an investigational product inventory and management system and may be integrated with the study database.

The Investigator or designee will be required to register the subject in the IWRS and may be prompted to provide subject data necessary to properly randomize and allocate the subject to treatment. A randomization number will be assigned (refer to [Section 9.5.2](#) below) and investigational product dispensing information (ie, bottle number[s]) will be provided.

9.4.1. Unblinding Procedures – Emergency Unblinding Procedures

Treatment assignment for individual subjects will be made available to the Investigator for medical emergency use only (such as unblinding which is necessary in order to treat an SAE) through the IWRS system. When possible, the Medical Monitor should be consulted in the event that a medical emergency necessitates unblinding (ie, in situations where knowledge of the blinded treatment assignment is necessary for further medical management of the subject). If it is not reasonable to inform the Medical Monitor in advance of the unblinding, the Investigator must promptly document in the subject's record the rationale for unblinding and should subsequently contact the Medical Monitor to explain any premature unblinding of treatment assignment. Procedures for unblinding a subject's treatment will be provided separately to the Investigator. Similarly, if the Medical Monitor breaks the blind for an individual subject for the purpose of evaluating an emergent safety issue, the Medical Monitor will document within trial documentation the rationale, circumstances, and the person or persons being informed about the unblinding.

The Data Monitoring Committee (DMC) will have access to the IWRS and will be able to unblind individual subjects. Refer to [Section 13.3](#) for further details regarding DMC access to blinded and unblinded data. The DMC will document details about any unblinded subject data reviews in the closed session DMC minutes, which will be made available to the Sponsor only after the database is locked and the trial is unblinded. Cases of premature unblinding, as noted above, will also be reviewed by the DMC.

Access to treatment assignments will also be made available to the designated Intercept staff responsible for expedited safety reporting of suspected unexpected serious adverse reactions (SUSARs) to the Regulatory Authorities.

9.5. Assignment of Site and Subject Numbers

9.5.1. Site Numbers

Each study site selected to participate in this study will be assigned a site number by the Sponsor. The site number will be used to categorize subject data and to identify the site and or Investigator within study documents. This number will be recorded in the CRF.

9.5.2. Subject Numbers

Subjects will be identified by a unique six-digit number, independent of the randomization number. The first three digits will represent the site number and the last three digits will represent the Screening number.

9.6. Restrictions

Participation in another investigational product, biologic, or medical device study within 30 days prior to Screening and during the course of the trial is prohibited.

9.7. Visit Procedures

9.7.1. Visit Windows

Visits should be based on Day 0 (not on the prior visit), eg, Month 3 should ideally occur 3 calendar months (± 2 weeks) following Day 0. The visit windows are as follows:

Visit or Procedure	Visit Window and/or Interval
Screening	Screening Visit 1 interval is 3 to 8 weeks prior to Day 0. Screening Visit 2 interval is 1 to 6 weeks prior to Day 0. The visit window for Screening 2 visits allows for the repeat biochemistry tests to be collected at least two weeks after the initial biochemistry sample was collected and will ensure ample time to receive lab results. The overall Screening interval is up to 56 days, but screening procedures should not be performed during the last 7 days of the window. See Section 9.7.6 for scenario specific visit windows that may be applicable at Screening.
Day 0	This is the day of randomization. On-treatment visit scheduling should be calculated from this point going forward. (The first dose of investigational product should be taken the next day, on Day 1.)
Month 1	+1 week (7 days)
Titration Visit – Standard Dosing Regimen	\geq Month 3
Titration Visit 1 – Modified Dosing Regimen	\geq Month 3
Titration Visit 2 – Modified Dosing Regimen	\geq 6 weeks after Titration Visit 1
Titration Visit 3 – Modified Dosing Regimen (Child-Pugh B ONLY)	\geq 6 weeks after Titration Visit 2

Visit or Procedure	Visit Window and/or Interval
Post-Titration Visit	1 month (+1 week [7 days]) from date of titration or after ≥ 3 months at a decreased dose or frequency
Month 3 to Month 12	± 2 weeks (14 days)
Quarterly visits (Months 15 to EOS)	± 2 weeks (14 days)
EOT (When subject discontinues investigational product)	As soon as possible upon study discontinuation and as near as possible to last dose taken
EOS (When subject terminates the study)	The final study visit; EOS will occur concurrent with EOT if a subject discontinues study medication at the time the subject's participation in the study ends (eg, withdrawal of consent or study termination by the Sponsor); EOS will occur after the EOT if the subject discontinues study medication but continues in the study.

EOS = end of study; EOT = end of treatment

9.7.2. Informed Consent Procedures

The Investigator or designee will explain the nature, purpose, possible risk and benefit of / study to the subject and will provide him/her with a copy of the written information and informed consent form (ICF). The subject will be given sufficient time to consider the study before deciding whether or not to participate. The subject will be informed that participation is voluntary and that her/his future medical treatment will not be compromised by participation in the study and that s/he can withdraw from the study at any time. The subject must be willing and able to provide written informed consent before entering the study. The Investigator or a medically qualified designee is responsible for administering and documenting the written informed consent of the subject. The subject will be given a copy of the written information and his/her signed and dated consent form.

Any change in a subject's consent status (eg, semi-annual telephone contact or medical record review) must be documented in a signed informed consent form or addendum. The subject will be given a signed and dated copy of the consent document.

9.7.3. Assessing Cirrhosis

9.7.3.1. Determination for Dosing Regimen

To determine which dosing regimen subjects should follow, the presence or absence of cirrhosis should be assessed by the Investigator at Screening Visit 1. Acceptable methods of confirming (via medical history) or assessing cirrhosis for purposes of determining dosing is defined as a subject who has documented evidence or presence of one or more of the following cirrhosis indicators:

- Biopsy results consistent with PBC Stage 4 ([Ludwig 1978](#))
- TE Median Value ≥ 16.9 kPa ([Corpechot 2012](#))
- The presence of any of the following (unless exclusionary per [Section 8.3](#)) in the absence of acute liver failure:
 - Varices
 - Ascites
 - Radiological evidence of cirrhosis (nodular liver or enlargement of portal vein and splenomegaly)
- Combined low platelet count ($<140\,000/\text{mm}^3$) with:
 - persistent decrease in serum albumin, or
 - elevation in prothrombin time /INR (not due to antithrombotic agent use), or
 - elevated bilirubin ($2\times$ ULN)

Subjects who exhibit no evidence of cirrhosis by the above methods of assessment will be dosed using the Standard Dosing Regimen, while those who do exhibit evidence of cirrhosis by one or more of the above methods will be dosed using the Modified Dosing Regimen according to their Child-Pugh Score calculated in the electronic case report form (eCRF) (see [Appendix A](#), [Section 7.3](#), [Table 3](#) and [Table 4](#)).

Cirrhosis status should be reassessed as clinically indicated throughout the study. Any change in cirrhosis status will necessitate re-evaluation of the dosing regimen.

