Because the liver is the primary site of action for the safety and efficacy of OCA, it is important to account for the differences in systemic and liver exposure when assessing effective doses. It is also important to note that while hepatically-impaired (Child-Pugh B and C) subjects treated with OCA in Phase 1 and 2 studies experienced plasma OCA exposures >10-fold higher than those in healthy subjects, no apparent impact on the overall safety profile was observed, consistent with only a modest increase in liver exposure of OCA associated with hepatic impairment. Collectively, the results from these analyses suggest that the doses of OCA administered to hepatically-impaired patients should be modestly lower than those for patients with normal hepatic function to achieve similar hepatic exposure.

Per the approved FDA prescribing label, the recommended dosing regimen for OCA in subjects with moderate and severe hepatic impairment is a starting dose of 5-mg OCA once weekly. Dosage adjustments in subjects with moderate (Child-Pugh B) or severe (Child-Pugh C) hepatic

impairment may be made after establishing tolerability at the lower dose (full modified dosing regimen is described in [Appendix A](#)).

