7. INVESTIGATIONAL PLAN

7.1. Overall Study Design

This is a Phase 4, double-blind, randomized, placebo-controlled, multicenter study. Eligible subjects will have a diagnosis of PBC with bilirubin levels of $>ULN$ and $\leq 5x ULN$ and/or ALP $>3x ULN$. Subjects enrolled will be at higher risk of liver-related clinical complications.

Approximately 428 subjects meeting all enrollment criteria will be recruited into the study over an approximate 4-year period, randomly allocated to treatment with either OCA or matching placebo in a 1:1 ratio (Figure 1). Subjects will be screened during a 1- to 8-week Screening period prior to entering the study to allow for the collection of repeat serum chemistry samples (at least 2 weeks apart) to confirm pretreatment ALP and total bilirubin values (refer to Section 9.7.6). Randomization will be stratified by UDCA treatment (yes/no) and baseline bilirubin categories ($>ULN/\leq ULN$). A minimum of 30% of subjects will have elevated bilirubin ($>ULN$) at Screening. In addition to the placebo control arm, multiple historical control groups (concurrent and retrospective) will be used.

Subjects will be dosed according to their cirrhosis status and Child-Pugh Score. Subjects who are noncirrhotic or classified as Child-Pugh A at Screening will initiate investigational product once daily with 5-mg OCA or matching placebo. Following 3 months of once daily treatment with investigational product, the dose should be titrated to a maximum 10 mg OCA or matching placebo once daily, based on tolerability and biochemical response (see Section 7.3).

[figure not shown]
Subjects with cirrhosis (see Section 9.7.3) and classified as Child-Pugh Class B or Child-Pugh Class C will follow a modified dosing regimen, and will initiate investigational product once weekly with the 5-mg OCA or matching placebo dose. In addition, these subjects will follow a modified titration plan, which is outlined in Appendix A.

It is anticipated that subjects will be followed for a minimum of approximately 6 years. The study will continue until approximately 127 adjudicated primary endpoint events have been accrued in unique subjects, or until the Sponsor (eg, based on advisement by the Data Monitoring Committee; DMC) terminates the study.

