7.3. Planned Dosing Regimen

Subjects will be randomized to treatment with either OCA or matching placebo in a 1:1 ratio. Subjects will be dosed according to their cirrhosis status (as defined in [Section 9.7.3](#)) and applicable Child-Pugh Score (see [Section 9.7.4](#)) as outlined in [Table 3](#).

Subjects who are noncirrhotic or classified as Child-Pugh A at screening will receive 5 mg OCA or matching placebo once daily for 3 months. Subjects should titrate to a maximum dose of 10 mg OCA once daily (or matching placebo) at the Month 3 visit or at any study visit following the Month 3 visit based on tolerability of the product and assessment of biochemical response. Up-titration should be considered when ALP and/or total bilirubin are >ULN. A review of safety laboratory results (eg, chemistry, hematology, and coagulation) obtained no more than 2 months prior to the planned up-titration visit must be completed as part of the product tolerability assessment before up-titration can occur (see [Section 7.4.1](#)).

For those subjects that up-titrate to 10 mg, dose may be decreased to 5 mg at any time during the study as considered clinically appropriate (eg, tolerability). Subjects may be titrated back up to a maximum dose of 10 mg once daily based on tolerability and clinical judgment of the Investigator. A review of safety laboratory results obtained within 2 months of the planned up-titration visit date is not required prior to re-challenging a subject up to 10 mg once daily dosing, as long as the decrease in dose/dosing frequency was less than 3 months in duration.

Table 3: Planned Dosing Regimen by Cirrhosis and Child Pugh Score

	Scheduled Dosing Regimen		
	Standard	Modified ^a	
	Noncirrhotic/ Child-Pugh A	Child-Pugh B	Child-Pugh C
Starting Dose^b (Day 0)	5 mg daily	5 mg once weekly	5 mg once weekly
Titration 1^c (≥Month 3)	10 mg daily	5 mg twice weekly ^d	5 mg twice weekly ^d
Titration 2^c (≥6 weeks after Titration 1)	NA	10 mg twice weekly ^d	10 mg twice weekly ^d
Titration 3^c (≥6 weeks after Titration 2)	NA	5 mg daily	NA

^a Refer to [Appendix A](#) for additional instructions regarding subjects following the Modified Dosing Regimen.

^b Starting dose based on subject's cirrhosis status and Child-Pugh score at Screening.

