^c Planned titration regimen is shown; however, the titration of dose and/or frequency is dependent on subject tolerability, biochemical response, and/or changes in cirrhosis status or Child-Pugh score at any time during the study (see Section 7.4).

^d Dosing per the twice weekly schedule must be at least 3 days apart.

The dosing regimen should be determined as described in Table 4. Investigators should follow the dosing/titration schedule as shown in Table 3.

Table 4: Determination of Dosing Regimen

Cirrhosis?	No	Yes	Yes	Yes
Child-Pugh Score	Any	A	B	C
Dosing Regimen	Standard		Modified for Child-Pugh B	Modified for Child-Pugh C

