Table 5: Changes in Dosing Regimen Due to Changes in Cirrhosis Status or Child-Pugh Score

Original Status	New Status ^a		
	Noncirrhotic OR Child-Pugh A	Child-Pugh B	Child-Pugh C
Noncirrhotic or Child-Pugh A	No Change	10 mg daily → 5 mg daily 5 mg daily → No change or 10 mg twice weekly ^b	5 mg or 10 mg daily → 10 mg twice weekly ^b
Child-Pugh B	5 mg daily → 10 mg daily	No Change	5 mg daily → 10 mg twice weekly ^b 10 mg twice weekly ^b → No change or 5 mg twice weekly 5 mg twice weekly ^b → No change or 5 mg once weekly
Child-Pugh C	10 mg twice weekly → 5 mg daily	10 mg twice weekly → 5 mg daily 5 mg twice weekly → No change or 10 mg twice weekly ^b 5 mg once weekly → 5 mg twice weekly	No Change

^a Once a subject begins dosing with the new dosing regimen, titration should occur as described for that dosing regimen in [Section 7.3](#) or Appendix A.

^b Dosing per the twice weekly schedule must be at least 3 days apart.

Subjects who exhibit development of cirrhosis at any point in the study should be assessed per [Section 9.7.3](#). If the presence of cirrhosis is confirmed and the subject's Child-Pugh score is either B or C, the appropriate modified dosing regimen should be followed. The dose or frequency of investigational product should be down-titrated to the next lowest dosing frequency in the appropriate modified dosing regimen unless the subject is currently taking a dose and frequency also specified in the modified dosing regimen and the Investigator determines that it is clinically appropriate for the subject to continue at that dose ([Appendix A](#)).

Subjects with pre-existing cirrhosis who demonstrate a change in the Child-Pugh Score from A to B or C at any point in the study should also have their dosing modified per the appropriate

dosing regimen. Changes in Child-Pugh Score that result from a transient, explainable change in laboratory parameters should be documented appropriately and should not necessarily result in a change to the dosing regimen ([Appendix A](#)).

Subjects who demonstrate an improvement in cirrhosis status or in Child-Pugh Score from B to A, or from Child-Pugh C to B, may be eligible to transition to the standard dosing regimen or the modified dosing for Child-Pugh B, respectively, based on tolerability. Prior to any dosing change, subjects must meet pre-titration assessment requirements for dosing as described in Section 7.4.1.

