APPENDIX A. MODIFIED DOSING REGIMEN FOR SUBJECTS WITH CHILD-PUGH B/C HEPATIC IMPAIRMENT

Overview of Modified Dosing Regimen for Subjects with Child-Pugh B or C Hepatic Impairment

An overview of the modified dosing regimen for subjects with Child-Pugh Class B or Child-Pugh Class C is presented in Figure 2 and Table 12.

Subjects who are cirrhotic and classified as Child-Pugh Class B or Child-Pugh Class C will initiate a modified treatment regimen with 5 mg OCA or matching placebo once weekly for at least 3 months. Subjects classified as Child-Pugh Class B should eventually titrate to a maximum dose of 5 mg OCA or matching placebo once daily, based on tolerability and biochemical response. Subjects classified as Child-Pugh Class C should titrate to a maximum dose and frequency of 10 mg OCA or matching placebo twice weekly.

Figure 2: Dosing by Cirrhosis Status and Child-Pugh Score

^a Cirrhosis may be assessed by histology or non-histological methods as defined in [Section 9.7.3](#).
BIW = twice weekly; QW = once weekly

Table 12: Planned Dosing Regimen by Cirrhosis and Child-Pugh Score

	Modified Dosing Regimen	
	Child-Pugh B	Child-Pugh C
Starting Dose^a (Day 0)	5 mg once weekly	5 mg once weekly
Titration 1^b (≥Month 3)	5 mg twice weekly ^c	5 mg twice weekly ^c
Titration 2^b (≥6 weeks after Titration 1)	10 mg twice weekly ^c	10 mg twice weekly ^c
Titration 3^b (≥6 weeks after Titration 2)	5 mg daily	NA

^a Starting dose based on subject’s cirrhosis status and Child-Pugh Score at Screening.

^b Planned titration regimen is shown; however, the titration of dose and/or frequency is dependent on subject tolerability and/or changes in cirrhosis status or Child-Pugh Score at any time during the study.

^c Dosing per the twice weekly schedule must be at least 3 days apart.

Modified Dosing Regimen for Subjects with Child-Pugh B Hepatic Impairment

Subjects with cirrhosis and classified as Child-Pugh B at Screening will follow a modified dosing schedule receiving 5 mg OCA or matching placebo once weekly as described in Figure 2. After a minimum of 3 months dosing once weekly with 5 mg OCA or matching placebo, and

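### Section 9.7.3.1 assigns every subject with cirrhosis to the Modified Dosing Regimen, while Table 4 and the rest of the protocol keep cirrhotic Child-Pugh A subjects on the Standard regimen

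*Protocol*

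**What the plan says.** Section 9.7.3.1 of the protocol lists the acceptable indicators of cirrhosis, to be assessed at Screening Visit 1, and then gives the dosing rule. Subjects with no evidence of cirrhosis receive the Standard Dosing Regimen, and subjects with any of the listed indicators "will be dosed using the Modified Dosing Regimen according to their Child-Pugh Score". The sentence ends with a reference to Appendix A, Section 7.3, Table 3 and Table 4.

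Other sections give the rule differently:

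- **Section 7.3, with Table 4:** "The dosing regimen should be determined as described in Table 4". Table 4 gives Standard for no cirrhosis and for cirrhosis with Child-Pugh A, and Modified for cirrhosis with Child-Pugh B or C.
- **Section 7.1:** "Subjects who are noncirrhotic or classified as Child-Pugh A at Screening will initiate investigational product once daily with 5-mg OCA or matching placebo".
- **Section 7.3, text:** "Subjects who are noncirrhotic or classified as Child-Pugh A at screening will receive 5 mg OCA or matching placebo once daily for 3 months".
- **Section 7.4, on cirrhosis that develops during the study:** if cirrhosis is confirmed and the "Child-Pugh score is either B or C, the appropriate modified dosing regimen should be followed".
- **Appendix A:** "Subjects who are cirrhotic and classified as Child-Pugh Class B or Child-Pugh Class C will initiate a modified treatment regimen".

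**The concern.** The two rules disagree for one group: subjects with cirrhosis who are Child-Pugh A. Section 9.7.3.1 puts them on Modified; the other sections put them on Standard. The conflict sits in the section headed as the determination of the dosing regimen, which the investigator applies before the first dose.

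The group is plainly eligible. A single indicator is enough to classify a subject as cirrhotic, including a transient elastography value of 16.9 kPa or more on its own. The exclusion criteria in Section 8.3 remove subjects with MELD above 12 or recent complications of cirrhosis, but not those with compensated cirrhosis.

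A Child-Pugh A subject randomized to OCA and placed on a Child-Pugh B or C schedule would be under-dosed relative to the design. Any dose-dependent treatment effect would be expected to be diluted in that subject.

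**Working it through.** The plan gives no figure to reproduce here. The check is a comparison of text, followed by arithmetic on the doses in Table 3.

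**Step 1. Regimen for a subject with cirrhosis and Child-Pugh A**

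| Place in the protocol | Regimen |
|---|---|
| Section 9.7.3.1 | Modified |
| Section 7.1 | Standard (5 mg once daily at start) |
| Section 7.3, text and Table 3 (Standard column covers noncirrhotic and Child-Pugh A) | Standard |
| Section 7.3, Table 4 | Standard |
| Section 7.4, pre-existing cirrhosis | Modified only on a move from A to B or C, so Standard before that |
| Section 7.4, Table 5 | Grouped with noncirrhotic |
| Appendix A, including Table 12 | Modified covers B and C only; a subject improving from B to A may return to Standard |

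Only 9.7.3.1 differs. Neither Table 3 nor Table 12 has a Modified column for Child-Pugh A, so the instruction in 9.7.3.1 cannot be carried out without borrowing another class's schedule.

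**Step 2. Which text is wrong**

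The dose rationale in Section 5.5.2.2 supports the majority reading: "the recommended dosing regimen for OCA in subjects with moderate and severe hepatic impairment is a starting dose of 5-mg OCA once weekly", which the same section equates with Child-Pugh B and C. Its simulations predict that plasma concentrations rise 1.4-fold in Child-Pugh A, against 8.0-fold in B and 13-fold in C. Liver concentrations rise 1.1-, 1.5- and 1.7-fold. Nothing there argues for a once-weekly start in Child-Pugh A.

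**Step 3. Size of the dose difference if a B/C schedule is used for a Child-Pugh A subject**

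Weekly dose = dose per administration × administrations per week, from Table 3.

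| Stage | Standard (mg/week) | Modified (mg/week) | Ratio |
|---|---|---|---|
| Start | 5 × 7 = 35 | 5 × 1 = 5 | 35/5 = 7 |
| After Titration 1 (Month 3 or later) | 10 × 7 = 70 | 5 × 2 = 10 | 70/10 = 7 |
| After Titration 2 (6 or more weeks later) | 70 | 10 × 2 = 20 | 70/20 = 3.5 |
| After Titration 3 (Child-Pugh B only, 6 or more weeks later) | 70 | 5 × 7 = 35 | 70/35 = 2 |

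On the Child-Pugh B schedule the subject reaches the Standard starting dose no earlier than 3 months + 6 weeks + 6 weeks, about 13 + 6 + 6 = 25 weeks, and never reaches 10 mg daily. On the Child-Pugh C schedule the ceiling is 20 mg per week, 3.5-fold below the Standard maximum.

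**The case against.** The strongest reply is that the sentence does not stand alone. It ties the regimen to the Child-Pugh Score and refers to Table 4, which gives the right answer. Section 7.3 already names Table 4 as the determining source. Section 9.7.4 says that the investigator should use both cirrhosis status and Child-Pugh score. With no Modified column for Child-Pugh A, a site looking up the dose finds that class only under Standard. Child-Pugh scores are also recalculated at every quarterly visit, which gives chances to catch an error. On this view the matter is one loose sentence, and the dose ratios describe a misreading whose frequency is unknown.

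Much of this stands, and it limits the likely harm. It does not make the sentence correct:

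- As worded, the reference to the Child-Pugh Score selects a version within Modified; it does not move a subject out of Modified.
- The reference to Table 4 leads to an instruction that contradicts the sentence containing it.
- Section 9.7.4 cites Table 6 for the regimen decision, but Table 6 is the scoring table and assigns no regimen.
- The quarterly recalculation is set up to detect a change in score. A subject who was Child-Pugh A from the start shows no change.

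It is also fair that the predicted liver concentrations alone do not fix the size of a dose cut: Child-Pugh B has only a 1.5-fold predicted rise and still starts once weekly. The case against Section 9.7.3.1 therefore rests on the agreement of the other sections, not on the exposure figures.

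**Conclusion.** The concern holds. Section 9.7.3.1 states the wrong rule for cirrhotic Child-Pugh A subjects, against the consistent rule in Sections 7.1, 7.3 and 7.4, Tables 3, 4 and 5, and Appendix A. It is a wording error in one operative sentence and should be corrected.

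The possible dose error is 7-fold at the start and after Titration 1, 3.5-fold after Titration 2, and 2-fold after Titration 3 on the Child-Pugh B schedule. These figures assume that a site follows the sentence literally and applies a Child-Pugh B or C schedule. The protocol does not say how many cirrhotic Child-Pugh A subjects are expected, so neither the number affected nor any dilution of the treatment effect can be estimated. The intent-to-treat primary comparison, the significance level, the power calculation and the 127-event target are formally unchanged.

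**What to change.** Replace the rule in Section 9.7.3.1 with wording to this effect: subjects without cirrhosis, and subjects with cirrhosis who are Child-Pugh A, use the Standard Dosing Regimen; only subjects with cirrhosis who are Child-Pugh B or C use the Modified Dosing Regimen, as set out in Table 4. Send a memo to sites stating the correction.

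The cost is a one-sentence protocol clarification and the memo. No analysis or sample size figure needs to change.
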